### **9.3 Analysis of Efficacy/Exploratory Endpoints**

Formal hypothesis testing and statistical analysis are not planned for this study.

### **9.4 Safety Analyses**

Device-related and procedure-related adverse effects (AEs) will be tabulated and analyzed. For a given AE term, counting will be done by subject, not by event, i.e. for a subject reporting the same AE more than once, the event will be counted only once, at the most severe and longest duration. The number and percentage of subjects experiencing each AE Term will be descriptively summarized.

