#### 4.1 Study Endpoints

##### 4.1.1 Safety Endpoint

- Incidence and severity of adverse device events.

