### 4.3.2 Safety Assessments

Following the first treatment, adverse events (AEs) will be assessed post-treatment and at each subsequent visit using the following scale:

- 1= mild: requires minimal or no treatment and does not interfere with the subject's daily activities.
- 2= moderate: may cause some interference with functioning.
- 3= severe: interrupts subject's usual daily activity and may require treatment.

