## 7.2 Recording AEs/ADEs and SAEs/SADEs

All AEs/SAEs or ADEs/SADEs will be: (1) evaluated and must be recorded in the subject's study case report forms (CRFs); (2) monitored and tracked from the time of the first treatment.

At each contact with the subject, the investigator must seek information on AEs/ADEs/SADEs by specific questioning and, as appropriate, by examination. AEs/ADEs/SADEs may be observed by the investigator and/or clinical research staff, elicited from the subject and/or family member or volunteered by the subject. All observed and volunteered adverse signs and symptoms, anticipated or unanticipated, regardless of severity or frequency, will be recorded in the case histories (medical chart and CRFs). Included in the description should be the nature of the sign or symptom, the date of onset, date of resolution (duration), the severity, anticipated or unanticipated, the relationship to study treatment or other therapy, the action taken (if any), and the outcome.

All SAEs/SADEs, anticipated or unanticipated, must be reported to Cutera immediately but not later than 5 working days. The SADE must be recorded in: (1) the CRF and (2) a written report must be submitted to Cutera within five (5) working days after the investigator first learns of the event and is to include a full description of the event and sequelae, in the format detailed by the Cutera Serious Adverse Event Form

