### **9.2 Analysis Sets**

The analysis sets will include all enrolled subjects who complete treatment.

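### Does the use of AE in section 9.4 leave the safety table ambiguous, or hide events judged unrelated?

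*Protocol*

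**What the plan says.** The safety endpoint in section 4.1.1 is "Incidence and severity of adverse device events". It is confined to device events.

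Section 9.4 gives the analysis in three sentences. The first sets the scope: "Device-related and procedure-related adverse effects (AEs) will be tabulated and analyzed". The second is a counting rule: each subject counts once per term, at the greatest severity and longest duration. The third names the display: "The number and percentage of subjects experiencing each AE Term will be descriptively summarized". That last sentence neither repeats nor lifts the restriction to related effects.

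Elsewhere the abbreviation is wider. Section 4.3.2 says that "adverse events (AEs) will be assessed post-treatment and at each subsequent visit", with no limit by cause. Section 7.2 lists adverse events and adverse device events, serious and non-serious, as separate labels. It requires that "All observed and volunteered adverse signs and symptoms, anticipated or unanticipated, regardless of severity or frequency, will be recorded", and the description of each event includes "the relationship to study treatment or other therapy, the action taken (if any), and the outcome". It also has all serious events reported to the sponsor, whether or not they are device effects.

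Section 9.1 sets 40 subjects for an exploratory pilot, and section 9.3 plans no formal testing.

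**The concern.** Two things catch the eye.

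First, one abbreviation has two expansions. Read with the meaning in section 9.4, the number and percentage per term cover related effects only. Read with the meaning in section 4.3.2, they cover everything. The counting rule inherits the doubt. If a subject has a mild related event and a severe unrelated event of the same term, the severity shown depends on the reading, and severity is part of the endpoint.

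Second, on the narrow reading the investigator's judgement of relatedness decides whether an event enters the only display named. That judgement can err either way, and a reader of the related-only table cannot see how many events were set aside. Safety is a stated objective of the study, so it is fair to ask whether an all-cause table should stand beside the related one.

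**Working it through.** No stated figure needs reproducing: the sample size of 40 comes with no error rate, power or precision target. The check is mainly a comparison of texts.

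**Step 1. Which meaning applies in section 9.4?**

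| Section | What it covers | Limited to related events? |
|---|---|---|
| 4.1.1, endpoint | adverse device events | yes |
| 4.3.2, assessment | adverse events | no |
| 7.2, recording | adverse events and device events, serious or not | no; relationship is recorded |
| 9.4, first sentence | device- and procedure-related effects | yes |
| 9.4, counting rule and display | AE term | not restated |

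Sections 4.3.2 and 7.2 govern collection, which should be broad. Sections 4.1.1 and 9.4 govern the endpoint and its summary, which are narrow. Within 9.4 the abbreviation is introduced in the first sentence and used in the next two, so the ordinary reading carries the restriction through. That reading covers the endpoint, with procedure-related effects added. The wider reading would require an analyst to replace the definition just given with one from another section.

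**Step 2. Is any information lost?** Under section 7.2 all events go on the case report form with severity, relationship and outcome. Both tables can be built from the same data. The wording affects the label on a table, not what is collected.

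**Step 3. How far could the reading or the label move a figure?**

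- Inputs: 40 subjects (section 9.1). Denominators of 35 and 30 are assumptions, because section 9.2 limits the analysis sets to subjects who complete treatment.
- Shift in one term's incidence when a subject's only event of that term is relabelled: 1/n. This gives 1/40 = 2.5 percentage points, 1/35 = 2.9 and 1/30 = 3.3. The shift is zero if the subject has another related event of the same term.
- Term seen in one subject: either 0/40 = 0% or 1/40 = 2.5%. The exact (Clopper-Pearson) 95% upper limit for 0/40 is 1 − 0.025^(1/40) = 8.8%. For 1/40 the exact interval is 0.1% to 13.2%. The two intervals overlap almost entirely.
- Assumed example of the two readings: if 4 of 40 subjects report a term and 2 of them are judged unrelated, the all-cause figure is 4/40 = 10.0% and the related figure is 2/40 = 5.0%. Both are correct answers to different questions. The endpoint asks the second.

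The 1/n shift is a property of any study of this size. It does not measure an effect of the wording, and the text gives no reason to expect a bias in one direction.

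**The case for a change.** The strongest case for acting is that this is an inconsistency in what the protocol states, not a detail left for later. Section 9.4 alone ties the abbreviation to related effects. The table of contents lists a separate definition of adverse event at 7.1.1, and the title of section 7 distinguishes adverse events from adverse device events. The visible text describes no comparison group, blinding or independent review of causality, so the relatedness label carries weight. The remedy would cost a sentence and one extra table from data already held.

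The first part stands: the abbreviation is used in two ways, and a careful editor would write adverse device effect in section 9.4. The rest carries less weight. Section 9.4 says what will be tabulated, not that nothing else will be. A list of safety tables is usual content for the analysis plan, which may exist but is not shown. The definitions in section 7.1 and much of section 6 are redacted, so nothing can be inferred from their absence. Any endpoint of device-related events rests on attribution, so dependence on that label comes with the endpoint and is not a fault of section 9.4. An all-cause table beside the related one is good practice, but no error in the plan makes it necessary.

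The extra sentence would not by itself guarantee an all-cause picture either. Section 9.2 states: "The analysis sets will include all enrolled subjects who complete treatment". Events in subjects who stop early could still fall outside the table. That is a separate question about the analysis set, and the abbreviation does not affect it.

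**Conclusion.** The concern is accurate as a remark on wording and does not call for a change to the plan. Followed as written, section 9.4 gives a sound descriptive summary of the endpoint in section 4.1.1, and the data for a wider table are collected in any case. The missing all-cause and serious-event tables are the kind of gap that the analysis plan or the analysts fill as routine. The double use of the abbreviation is a clerical slip that alters no result in an exploratory pilot without formal testing.

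The most that turns on one subject's label is 2.5 percentage points for one term with 40 subjects, or up to 3.3 points if only 30 complete treatment (an assumed count), in no known direction.

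This rests on two assumptions: that the local definition in section 9.4 governs its own paragraph, and that the redacted definitions in section 7.1 do not contradict it.

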##### 4.1.2 Exploratory Endpoints

- [REDACTED]

- GAIS at 12 weeks post first and final treatment from Baseline.

- [REDACTED]

- [REDACTED]

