#### Treatment-related Discomfort:

After each treatment, subjects will be asked to rate the average amount of discomfort experienced during treatment and immediately after treatment using the Pain Rating Scale (VAS Scale) Appendix 2.

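### Does counting a repeated adverse event once, at its worst severity and longest duration, distort the safety summary in Section 9.4?

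*Protocol*

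**What the plan says.** Section 9.4 of the protocol sets out the safety summary. On scope it says "Device-related and procedure-related adverse effects (AEs) will be tabulated and analyzed". On the unit of analysis it says "counting will be done by subject, not by event", and for a term that the same subject reports again, "the event will be counted only once, at the most severe and longest duration". The one statistic it then names is the number and percentage of subjects with each term, summarised descriptively.

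The safety endpoint, in Section 4.1.1, is "Incidence and severity of adverse device events". Section 7.2 governs data collection and is wider: "All observed and volunteered adverse signs and symptoms, anticipated or unanticipated, regardless of severity or frequency, will be recorded". The description of each sign or symptom is to include "the date of onset, date of resolution (duration), the severity, anticipated or unanticipated, the relationship to study treatment or other therapy".

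Subjects may have more than one treatment. Section 4.1.2 lists "GAIS at 12 weeks post first and final treatment from Baseline", and the paragraph on discomfort in Section 4.3.2 begins "After each treatment, subjects will be asked to rate the average amount of discomfort". The number of treatments is redacted.

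**The concern.** Three features of Section 9.4 invite criticism.

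- **Pairing.** The rule takes two maxima, worst grade and longest duration, without saying that they belong to one occurrence. If they come from different occurrences, a single record built from both describes an event that nobody had. The duration attached to the worst grade could then be too long but never too short.
- **Recurrence.** With one count per subject and term, a reaction that returns at re-treatment looks the same as one that occurred once. In a device study where re-treatment is possible, a reader may want to know the difference.
- **Scope.** Section 7.2 records all adverse signs and symptoms with their relationship to treatment, while Section 9.4 names only device- and procedure-related effects. The visible text describes no control group, so a reader of the planned table could not see what had been judged unrelated.

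At stake would be a descriptive safety table that misstates how long severe reactions last, hides how often they recur, and depends on unverified attribution. No formal testing is planned (Section 9.3), so the descriptive tables carry the safety result.

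**Working it through.** The protocol derives no figure on this point, so there is none to reproduce. The check applies the rule to small examples and then sets the result against the endpoint.

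**Inputs.** The planned number is 40 subjects (Section 9.1). The grades are 1 mild, 2 moderate and 3 severe (Section 4.3.2). The durations, the number of affected subjects and the number of treatments below are assumptions for illustration. All 40 subjects are assumed to be in the analysis set.

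**1. Pairing.** For a subject with several occurrences of a term, a paired record would overstate the duration of the worst-grade event by

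longest duration over all occurrences − duration of the worst-grade occurrence.

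This is zero or positive.

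- Severe for 2 days and mild for 30 days: 30 − 2 = 28 days, a ratio of 30/2 = 15.
- Mild for 2 days and severe for 30 days: 30 − 30 = 0 days.

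The excess therefore depends wholly on the durations chosen, and it vanishes whenever the worst occurrence is also the longest. It also needs a table that shows grade and duration as one record. If the two maxima are summarised separately, the same subject contributes a worst grade of severe and a longest duration of 30 days. Both statements are true.

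**2. Effect on the endpoint.** In either example, and under either reading, the subject adds 1/40 = 2.5% to the incidence of the term and is graded severe. Incidence and maximum severity do not change.

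**3. Recurrence.** Compare two cases:

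- Four subjects with one event each: 4 × 1 = 4 events, incidence 4/40 = 10%.
- Four subjects with one event at each of two treatments: 4 × 2 = 8 events, incidence 4/40 = 10%.

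The event count doubles and the incidence does not move. But 10% is the correct proportion of subjects affected in both cases. The comparison shows that an incidence does not measure event burden. It does not show that the incidence is wrong.

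**4. Sections 7.2 and 9.4 side by side.** The phrase on severity and frequency in Section 7.2 determines what is written in the chart and case report form. It makes no commitment on what is tabulated. Section 9.4 commits to tabulating related effects, which matches an endpoint of adverse device events, and it does not say that nothing else will be tabulated. The two sections do not contradict each other. Because onset, resolution, severity and relationship are recorded, an event-level listing or an all-cause table can be produced from the same data.

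**The case for a change.** The strongest case for a change rests on the pairing. Here the protocol is not silent. It states a rule, the rule has two readings, and two analysts could produce different tables from the same data. A later analysis plan that repeated the words would inherit the ambiguity. Section 9.4 itself brings duration in, so it should say what the reported duration means. In a study without formal testing, the records behind the safety table should describe real events. All the data needed are already collected, and the repair is one clause.

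Part of this stands. The wording is ambiguous, and a paired record could only err towards overstating the duration of the worst event. But the harm requires both the less sensible of the two readings and a display of grade with duration that the visible text does not plan. No visible threshold, stopping rule or decision uses duration. An analyst who needed to report it would either give the two maxima separately or take the duration of the most severe occurrence, and both can be obtained from the recorded data.

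The arguments on recurrence and scope are weaker. Counting by subject is the right convention for an incidence, and tabulating related effects fits the stated endpoint. Per-term event counts and all-cause tables are useful additions, but a protocol commonly leaves them to the statistical analysis plan. An all-cause table would show which events were judged unrelated, but it would not supply the missing comparator. Two limits also apply to what can be argued: the number of treatments is redacted, and so are the definitions in Section 7.1.

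**Conclusion.** The concern does not call for a change. What remains of it is a loose phrase: Section 9.4 does not say whether worst severity and longest duration describe one occurrence or are two separate summaries per subject. An analyst can settle that sensibly without altering any result the protocol plans. The safety endpoint, incidence and severity by subject, is correct under either reading. The missing event count and all-cause table are additional outputs, and their absence is not an error.

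The effect on the endpoint is nil. The possible effect on a reported duration runs from 0 days upwards (28 days in the assumed example), and no value for the trial can be derived from the document. The conclusion rests on three assumptions: that the summary is the one Section 9.4 names, that no redacted passage bases a decision on duration or number of events, and that individual occurrences are recorded as Section 7.2 requires.

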## **10 STUDY MANAGEMENT AND ADMINISTRATIVE PROCEDURES**

[REDACTED]

[REDACTED]

[REDACTED]

[REDACTED]

[REDACTED]

[REDACTED]

[REDACTED]

### **10.3 Protocol Compliance**

The principal investigator must comply with all terms of the protocol.

#### **10.3.1 Protocol Amendments**

Neither the principal investigator nor the sponsor will modify or alter this protocol without first obtaining the concurrence of the other party (with the exception of amendments which involves mitigating a medical emergency or immediate health risk to the subject). The party initiating an amendment must confirm it clearly in writing and it must be signed and dated by the sponsor and the principal investigator. IRB approval must be obtained before implementation of an amendment.

[figure not shown]
[figure not shown]
[figure not shown]
#### **10.3.2 Protocol Deviations**

All protocol deviations must be clearly described on the case report form (i.e., Cutera Protocol Deviation Form). Deviations from the protocol may include but are not limited to subject's failure to attend scheduled visit during a visit window, and incomplete or incorrect study procedures. Any medical emergency or immediate health risk to the subject which results in a protocol deviation and must be reported to the sponsor within 5 working days

Significant protocol deviations must be reported to IRB according to their policies.

### **10.5 Subject Confidentiality**

This study preserves the confidentiality of all subjects under the Health Insurance Portability and Accountability Act of 1996 (HIPAA) Privacy Rule. The following safeguards will be in place to protect the privacy of the individuals who are the subjects of the health information to be used in the research and the confidentiality of that information:

not be disclosed.

### **10.6 Publication Policy**

The investigator shall have the right to publish the results of the study. Unless mutually agreed upon in writing, prior to submission for publication of any manuscript, poster, presentation, abstract or other written or oral material describing the results of the study, the investigator shall allow sponsor to review manuscript, poster presentation, abstract or other written or oral material which describes the results of the study for the purpose only of determining if any patentable information is disclosed. At the sponsor's request, the investigator shall withhold any publication or presentation to permit sponsor to seek patent protection and to remove any confidential information from all publications.

A series of 12 horizontal black bars of varying lengths, decreasing from left to right. The bars are positioned in a staggered, non-linear pattern across the frame. The first bar is the longest and is located at the top left. Subsequent bars are shorter and are positioned further to the right, creating a sense of depth and movement. The bars are set against a white background.

11 of 11 pages

A series of eight horizontal black bars of varying lengths, each preceded by a small white rectangular gap. The bars are arranged vertically, with the first bar being the longest and the eighth being the shortest. The gaps are positioned at the start of each bar.

[REDACTED]

[REDACTED]

For more information, contact the Office of the Vice President for Research and Economic Development at [contact] or [[contact]](mailto:[contact]).

THE JOURNAL OF CLIMATE

1

For more information, contact the Office of the Vice President for Research and Economic Development at [contact] or [[contact]](mailto:[contact]).

© 2000 by the American Psychological Association or the National Council on Measurement in Education.

1

For more information, contact the Office of the Vice President for Research and the Office of the Vice President for Student Affairs.

1

10.1002/anie.201907002

1

For more information, contact the Office of the Vice President for Research and Graduate Studies at [contact] or [[contact]](mailto:[contact]).

1

1

For more information, contact the Office of the Vice President for Research and Economic Development at [contact] or [[contact]](mailto:[contact]).

1

For more information, contact the Office of the Vice President for Research and Economic Development at [contact] or [[contact]](mailto:[contact]).

1

1

Black box

1

Digitized by [contact]

[REDACTED]

[REDACTED]

[REDACTED]

[REDACTED]

[REDACTED]

[REDACTED]

[REDACTED]

[REDACTED]

[REDACTED]	[REDACTED]

[REDACTED]

[REDACTED]
